4.6.3. Analyses of Key Secondary Efficacy Endpoints

For the primary estimand for key secondary efficacy endpoints defined in [Table 1](#), off-study treatment data up to Week 16 will be included in the analysis, and subjects will be considered as non-responders after usage of prohibited/rescue medications that impact efficacy analyses. Additionally subjects with missing data at Week 16 will be defined as non-responders. The analyses will use CMH test adjusted by randomization stratification variables: sex and years since the first nodule observed (i.e., ≥ 10 years vs. < 10 years). Response rate difference adjusted to stratification factors between each KPL-716 dose group and placebo will be derived. In addition, odds ratio and the corresponding 95% confidence intervals (CI) will be provided along with the p-values.

4.6.4. Analysis of Other Efficacy Endpoints

The primary estimand for continuous endpoints of change and percent change from baseline specified as secondary and exploratory endpoints will be defined and analyzed as the primary estimand for primary efficacy endpoints. If some extreme small values are observed at baseline for a parameter, percent changes will not be summarized for that parameter due to inflated percent change. For example, preliminary data showed values of 0 for some subjects in sleep loss VAS.

The primary estimand for binary responder endpoints over time including week 16 will be defined and analyzed as key secondary efficacy endpoints above.

4.6.5. Subgroup Analysis

The primary and key secondary efficacy endpoints may be summarized by subgroups listed in [Table 8](#) based on the mITT analysis set.

Table 8: Subgroups Defined at Baseline

Subgroup	Categories
Age group	<65 years, ≥ 65 years

Subgroup	Categories
Sex	Female, Male
Race	White, Black, Other
Ethnicity	Hispanic or Latino, Not Hispanic or Latino
Years since the first nodule observed	≥10 years, <10 years
Elevated IgE at Baseline	High (>200 IU/mL), normal (≤200 IU/mL)
Anxiety or depression at baseline	Yes, No

4.6.6. Rescue medications and prohibited medications

Rescue medications are allowed under specific guidance as specified in Pharmacy Manual Version 3.0, Dated 06 October 2021 ([Table 9](#)).

Table 9: Rescue medications listed in pharmacy manual

Tier 1	Antihistamines, oral: 
 • Diphenhydramine • Cetirizine
Tier 2	
 • Hydrocortisone ointments, up to 2.5% • Desonide cream, lotion 0.05%
Tier 3	Non-Europe countries 
 • Triamcinolone acetonide, 0.1% • Fluocinolone Acetonide, 0.025% Europe countries 
 • Fluticasone propionate cream/ointment, up to 0.05%
Tier 4	Clobetasol propionate, 0.05%

For analysis purpose, TCS, oral/IV antihistamines, topical antihistamine, corticosteroid intralesional injection, and/or systemic corticosteroids, which were used to reduce pruritus or treat PN skin lesion on and after first dose date and have significant impact on efficacy interpretation, are defined as rescue medications. TCS which are deemed to have minimum impact on efficacy interpretation are not considered as rescue medications. For example, TCS used for injection site reactions which are not overlapping with the subject's PN lesions are not considered as rescue medication. Antihistamines targeting H2 receptor are not considered as rescue medications due to no impact on pruritis. Identification of rescue medications will be based on medical review in a blinded way before database lock.

Additionally, the protocol specified a list of medications which are prohibited from designated timepoints before Day 1 and throughout the study. Prohibited medication which impact on efficacy analyses will be identified based on blind medical review before database lock as well.

Number of subjects who used rescue/prohibited medications and days on rescue/prohibited medications will be summarized by study periods. Rescue/prohibited medications which overlap with both DB and OLE periods will be summarized based on proportion of days in each period. Use of rescue/prohibited medications over time will be summarized by weeks which will be defined consistently as weeks of WI-NRS. Time to 1st use of rescue/prohibited medications will be summarized based entire study period.

4.7. Safety Analyses

Safety analyses will consist of data summaries for clinical and laboratory parameters, vital sign, and for adverse events (AEs). Adverse events will be coded using MedDRA of the version at database lock. Laboratory parameters, vital signs, and ECG data will be summarized as descriptive statistics by treatment, visit, and study period. Safety summaries will be based on the safety analysis set.

4.7.1. Adverse Events

Adverse events will be mapped to PT and SOC using the most up to date MedDRA of the version at database lock. A treatment-emergent AE (TEAE) is defined as any event not present before exposure to study drug or any event already present that worsens in either intensity or frequency after exposure to study drug. Furthermore, if an AE cannot be determined as treatment-emergent due to incomplete/missing date, conservatively, it will be considered as treatment emergent and included in the summary tables. For subjects who enter OLE, TEAEs which occur (based on AE start dates) before OLE first dose date will be summarized into DB period, otherwise into OLE period. If AE occurring time is available, time should be compared to OLE first dose date and time for AE period derivation.

The following TEAE summaries will be summarized as an overview.

- Any TEAEs
- Drug-related TEAEs
- TEAE by maximum severity (mild, moderate, severe)
- Serious TEAEs (SAEs)
- Drug related serious TEAEs
- TEAEs leading to dose interruption
- TEAEs leading to treatment discontinuation
- TEAEs leading to study discontinuation
- Death
- TEAE of special interest

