### 7.5.3 Clinical Laboratory Evaluations

Blood and urine samples will be collected for clinical laboratory evaluations (including clinical chemistry, hematology, urinalysis, and serology) at the time points specified in [Appendix 1](#).

Subjects will be asked to provide urine samples for a drugs of abuse screen at the Screening Visit and Day 1 prior to dosing and at any time during the study at the discretion of the Investigator and in consultation with the Sponsor, if needed.

For all female subjects of childbearing potential, the serum pregnancy test will be performed at the Screening Visit and the urine pregnancy test will be performed at the designated timepoints in [Appendix 1](#). Dosing should not proceed if urine pregnancy test is positive, until a negative serum pregnancy test is confirmed. Postmenopausal status will be confirmed via FSH testing at Screening.

An Investigator will perform a clinical assessment of all clinical laboratory test results.

After Screening, any clinically significant abnormal findings should be reported as AEs.

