 On dosing days, all blood samples (safety, PK, ADA, biomarkers, serum pregnancy if indicated, etc.), all urine samples (urinalysis, pregnancy, urine drug screen if indicated), all efficacy assessments (Sleep Loss VAS, PN-NAT, PN-IGA, etc.), all patient reported outcomes (ItchyQoL, PHQ-9, GAD-7), all medical photography, ECG and/or skin biopsies will be performed prior to dosing. Subjects will be randomized to receive KPL-716 or placebo on Day 1. Subjects will be observed for 1 hour after each dosing. Vital signs will be measured at the end of the 1-hour observation period and adverse events will be recorded if any. In case study drug treatment is interrupted or discontinued, subjects should continue with study visits as outlined in the Schedule of Activities, minus dosing. In case of early withdrawal, subjects will follow the schedule of activities for the EOS Visit (Week 52).

 At the Screening Visit, subjects will be instructed through ASR and PRR training to evaluate the intensity of their WI-NRS on a daily basis. The ASR and PRR training should be repeated monthly until Week 12 or as needed. The daily recordings can begin any time after the Screening Visit. Eligible subjects will continue daily recording of WI-NRS and rescue medication use from Day 1 through the EOS Visit.

 At the Screening Visit, medical photographs will be taken of the representative area of subject's disease as determined by the PI. The same representative area will be followed over time. In addition, whole body medical photographs will be captured (upper front and lower front, upper back, and lower back) without the face and with the genitals covered. Confirmation of diagnosis of PN will be performed by review of medical photographs (Refer to Study Manual) prior to each subject's randomization.

 Skin biopsies will be collected pre- and post-treatment during the study. Skin biopsies are optional. A medical photograph of the location of the biopsies (prior to biopsies) will be taken.

 Blood samples for biomarkers include serum sample(s) and whole blood sample(s) for each individual patient.

 PK blood samples will be collected prior to study drug administration on dosing days.

 This study drug administration (which is part of the OLE) will only occur if subjects elect to be in the OLE.

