3.3. Analysis Visits and Study Period

For efficacy analyses, DB period is defined from randomization up to the first OLE dose if subjects enter OLE treatment period, or end of study in subjects not enrolled in OLE period, unless specified. OLE period is defined from OLE first dose up to the end of study. If assessment time is available, assessments should be further differentiated by time compared to OLE first dose. If assessments are collected on the same day as OLE first dose date and no assessment times are available, those assessments should be counted into DB period.

For safety analyses, DB period is defined from first dose up to the first OLE dose if subjects enter OLE treatment period, or end of study if subjects not enrolled in OLE period.

Efficacy assessments

For the efficacy assessment, the reference date for the derivation of relative days of events or findings will be the randomization day. If a subject receives treatment dose prior to the randomization by mistake, the reference date of efficacy assessment will be the date of the first treatment dose administration for that subject.

For the daily WI-NRS, weekly average will be aligned by study periods. For DB period, weekly average will be calculated based on every 7 days increment starting on Day 1. For week 16, only assessments before the first dose of OLE period will be included for weekly average calculation. Time windows are specified in [Table 2](#) below.

Table 2: Time window of weekly average WI-NRS in DB period

Analysis week	Time windows referring to randomization date
Baseline	-7 to -1
Week 1	1 - 7
Week 2	8 - 14
Week 3	15 - 21
Week 4	22 - 28
Week 5	29 - 35
Week 6	36 - 42
Week 7	43 - 49
Week 8	50 - 56

Week 9	57 - 63
Week 10	64 - 70
Week 11	71 - 77
Week 12	78 - 84
Week 13	85 - 91
Week 14	92 - 98
Week 15	99 - 105
Week 16	106 - min(113, Day of OLE first dose)

The time window of weekly average NRS in OLE period will start from the day after the first dose of OLE period as specified in [Table 3](#).

Table 3: Time window of weekly average WI-NRS in OLE period

Analysis week	Time windows referring to OLE first dose date
Week 17 - OLE	2 - 8
Week 18 - OLE	9 - 15
Week 19 - OLE	16 - 22
Week 20 - OLE	23 - 29
Week 21 - OLE	29 - 36
Week 22 - OLE	37 - 43
Week 23 - OLE	44 - 50
Week 24 - OLE	51 - 57
Week 25 - OLE	58 - 64
Week 26 - OLE	65 - 71
Week 27 - OLE	72 - 78
Week 28 - OLE	79 - 85
Week 29 - OLE	86 - 92
Week 30 - OLE	93 - 99
Week 31 - OLE	100 - 106
Week 32 - OLE	107 - 113

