		Physical examination, Vital signs, Body weight, Clinical lab blood tests	ECG Pregnancy test	Urinalysis
Baseline*	1	ADA	≤ 1	≤ 1
Week 2	15		2 - 22	
Week 4	29		23 - 43	

Week 8	57	44 - 71	2 - 85
Week 12	85	72 - 99	
Week 16	113	100 - OLE first dose	86 - OLE first dose 2 - OLE first dose

* up to first dose date/time

The visit mapping in OLE period will start from the day after the first dose of OLE period using the time window specified in [Table 7](#).

Table 7: Time window for safety variables in OLE period

Visit	date	Time windows		
		Physical examination, Vital signs, Body weight, Clinical lab blood tests	ECG	Urinalysis, Pregnancy test
Target Day referring to OLE first dose	ADA			
Week 18 - OLE	15	2 - 22		
Week 20 - OLE	29	23 - 71		
Week 32 - OLE	113	72 - 169		2 - 169
Week 48 - OLE	225	170 - 239		170 - 239
Week 52 - OLE	253	240 - EOS	2 - EOS	240 - EOS

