4.3. Prior and Concomitant Medications and procedures

4.3.1. Prior and Concomitant Medications

All medications will be coded using the World Health Organization (WHO) Drug Dictionary of the version at database lock.

Prior medications are defined as medications that started before the first dose of study drug. Concomitant medications are defined as medications that (1) started before the first dose of study drug and continued into the treatment period, or (2) started on or after the date of the first dose of study drug. The number (%) of subjects who took prior and concomitant medications will be summarized on the anatomical class (ATC level 3) and PT by treatment and overall subjects. For subjects who enter OLE, concomitant medications which start on or before OLE 1st dose will be summarized into DB period, otherwise into OLE.

Prior Topical corticosteroid (TCS) regardless of indication, systemic corticosteroid, intralesional corticosteroid, and oral antihistamine will be summarized as well, of which identification will be based on medical review.

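### Untimed adverse events that report pre-dose Week 16 findings are tabulated in the open-label period, contrary to the SAP's own end of the double-blind period

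*SAP*

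**What the plan says.** SAP 4.7.1 places the TEAEs of OLE entrants in two steps. The first uses the date: "TEAEs which occur (based on AE start dates) before OLE first dose date will be summarized into DB period, otherwise into OLE period". The second refines it: "If AE occurring time is available, time should be compared to OLE first dose date and time for AE period derivation". No separate rule covers an event dated to the day of the first OLE dose with no time, so the date sentence decides, and it gives OLE.

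OLE dosing starts at the Week 16 visit (Protocol 4.4; Appendix 1, footnote 13). Appendix 1, footnote 7, puts that day's blood samples, urine samples and ECG ahead of the injection: "ECG and/or skin biopsies will be performed prior to dosing". Protocol 4.1.2.2 says the same of dosing-day procedures in general and lists the physical examination among them.

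Findings from these checks become AEs. For laboratory results, Protocol 7.5.3 says: "After Screening, any clinically significant abnormal findings should be reported as AEs". Protocol 7.5.5 does the same for new clinically significant ECG abnormalities. Protocol 8.7.4 and SAP 4.7.5 do so for physical-examination findings.

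Elsewhere the SAP treats the day of the first OLE dose as follows:

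- **Safety DB period (3.3):** it ends at the first OLE dose for subjects who enter the OLE.
- **Safety visit windows (3.3, Table 6):** the DB Week 16 windows for ECG and urinalysis are "86 - OLE first dose 2 - OLE first dose", and the laboratory, vital-sign and examination window closes at the same point. OLE mapping starts the next day (Table 7).
- **Efficacy assessments on that date (3.3):** where "no assessment times are available, those assessments should be counted into DB period".
- **Medications (4.3.1):** "concomitant medications which start on or before OLE 1st dose will be summarized into DB period, otherwise into OLE".

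**The concern.** The end-of-DB safety checks and the first OLE dose share one visit, with the checks first. A clinically significant abnormality found at those checks arose under double-blind treatment. If the AE record carries the visit date and no clock time, 4.7.1 nevertheless files it under open-label 360 mg Q2W. For a placebo subject, an event that preceded any KPL-716 in this trial would appear in a table of events on KPL-716.

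The DB period is the only placebo-controlled part of the safety evaluation. A finding made at its closing visit belongs there by the SAP's own definition. Under the present wording one Week 16 result can be a DB laboratory value, and a medication started for it that day a DB medication, while the AE that reports it is an OLE event. Only OLE entrants are affected, so two subjects with the same Week 16 finding can be counted in different periods according to whether they continued.

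**Working it through.** The point concerns a classification rule, so the check is to apply each rule to the same dates.

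**Inputs**
- First OLE dose at the Week 16 visit, nominally Day 113 (Protocol Appendix 1). SAP 4.5 allows up to 17 OLE doses. Dosing every 2 weeks from Week 16 to Week 48 gives (48 − 16)/2 + 1 = 17, so the count agrees with a first OLE dose at Week 16.
- Week 16 blood, urine, ECG and examination done before that dose (Protocol 4.1.2.2; Appendix 1, footnote 7).
- A test clock time of 12:00 for the dose, chosen only to exercise the rule.

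**Results** (the measurement and medication columns are read at date level)

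| Record | AE period (SAP 4.7.1) | Laboratory or ECG value (Tables 6 and 7) | Medication start (SAP 4.3.1) |
|---|---|---|---|
| Day 112, no time | DB | DB | DB |
| Day 113, no time | **OLE** | DB | DB |
| Day 113, 09:00 | DB | DB | DB |
| Day 113, 15:00 | OLE | DB | DB |
| Day 114, no time | OLE | OLE | OLE |

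The second and third rows show the fault. A finding made at 09:00, before the dose, is DB if the hour was entered and OLE if it was not. SAP 3.3 makes it DB in both cases, because the safety DB period ends at the dose and not at the start of that calendar day.

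**Size.** The documents do not say how many AEs lack an onset time or how many subjects enter the OLE, so only an illustration is possible. Assume that 85% of 45 subjects per arm enter the OLE. The 85% is borrowed from the 15% drop-out in the sample-size section; entry is optional and could be lower. That is 45 × 0.85 = 38.25 per arm, or 4 × 38.25 = 153 in all. Let a proportion p of entrants have an untimed AE dated to the Week 16 visit:

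| p (assumed) | Placebo entrants, 38.25 × p | All arms, 153 × p |
|---|---|---|
| 2% | 0.8 | 3.1 |
| 5% | 1.9 | 7.7 |
| 10% | 3.8 | 15.3 |

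Only the part of these AEs that reports a pre-dose finding is misplaced, so each figure is a ceiling at its assumed rate.

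**The case against.** **Recorded times resolve many cases.** Protocol 7.5.1.1 asks for the time of onset of every AE, and 4.7.1 uses a time when there is one. This stands and narrows the point to untimed AEs. It does not close it: the protocol does not say that a clock time is meant, the SAP itself makes the time conditional, and a laboratory abnormality often has no observable hour of onset.

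**OLE is a defensible default for an untimed dose-day AE.** Unlike a pre-dose measurement, an AE can begin after the injection. Subjects are observed for an hour after dosing with AEs recorded, and injection site reactions or angioedema (the AESI) could plausibly follow the dose. This also stands. The efficacy and medication rules are therefore not a full precedent for AEs. The contradiction is confined to AEs that report something found before the dose.

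**The controlled comparison of the measurements survives.** Week 16 laboratory and ECG values stay in DB and feed the laboratory shift tables by period (SAP 4.7.2) and the ECG shift and QTcF summaries (SAP 4.7.4). This stands. Only the period label of an AE record moves, and that label is not a causality assessment, which the investigator makes separately.

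**A stronger reading about undated events.** A reader might infer that the catch-all clause also sends AEs with no usable start date to the OLE, and that they should default to DB. The SAP says that "if an AE cannot be determined as treatment-emergent due to incomplete/missing date, conservatively, it will be considered as treatment emergent", but this settles only whether the event is treatment-emergent. The period sentence works on start dates and is silent when there is none. Nor is a DB default clearly better. After randomization the OLE covers 36 of 52 weeks for an entrant who completes it. At a constant AE rate (an assumption) 36/52 = 69% of undatable events would truly be OLE events, and a DB default would put them into the controlled comparison.

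**Conclusion.** The inconsistency is real and narrow. For OLE entrants, an untimed AE that reports a pre-dose Week 16 finding and is dated to the first-dose day is tabulated as OLE. SAP 3.3 and Table 6 place both the moment and the measurement in DB. The consequence is a period misclassification of probably few AE records in descriptive safety tables.

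This rests on three conditions: the first OLE dose falls on the same date as the Week 16 checks, the AE is dated to that visit (the documents do not say how a laboratory AE is dated), and no onset time is recorded.

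Three further inferences are not supported:

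- **Share of AEs.** From Table 6, Week 16 is 1 of 5 post-baseline DB laboratory and examination windows (20%), 1 of 2 ECG windows (50%) and the only urinalysis window (100%). These are shares of scheduled assessment windows, not of AEs, many of which come from open questioning or spontaneous report.
- **Bias between arms.** The rule is the same in every arm, and nothing in the documents shows that OLE uptake or untimed reporting will differ by arm.
- **No prior KPL-716.** Placebo entrants have had none in this trial before the first OLE dose, but SAP 4.2.2 tabulates treatment in previous KPL-716 studies.

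**What to change.** Add one rule to SAP 4.7.1, to this effect: for subjects who enter the OLE, an AE with no onset time that is dated to the OLE first-dose day and reports a finding from a pre-dose Week 16 laboratory, urinalysis, ECG, vital-sign or physical examination is counted in DB, with the recorded assessment time used where available; all other untimed AEs of that day remain in the OLE. The restriction to pre-dose measurements matters for vital signs, which are also taken after dosing. No rule that defaults undated AEs to DB is proposed.

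The cost is a sentence in the SAP, a small programming change, and a short blinded review of AE records dated to the first-dose day. The documents show no field that links an AE to the assessment that revealed it, so the review is needed to identify these records. It should be done before the database lock for the DB analysis. SAP 4.6.6 already plans a blinded medical review of rescue and prohibited medications before lock, and this could be done alongside it.

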#### **4.2 Duration of Phase 2b**

The planned study duration per subject for Phase 2b will be approximately 56 weeks including a maximum of 4 weeks for the Screening Period, 16 weeks for the Double-Blind Period, and 36 weeks for the OLE Period.

The minimum duration for the Screening Period will be 7 days.

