## **7.5 Safety and Tolerability Assessments**

### **7.5.1 Adverse Events**

#### **7.5.1.1 Adverse Event Definition and Categorization**

The investigator is responsible for collecting all AEs that are observed or reported during the study from the time the subject signs the ICF through the EOS Visit, regardless of their relationship to study drug or their clinical significance.

An AE is any untoward medical occurrence in a subject or clinical investigation subject administered a pharmaceutical product, which does not necessarily have a causal relationship with this treatment. An AE can therefore be any unfavorable and/or unintended sign (including an abnormal laboratory finding), symptom or disease temporally associated with the use of a medicinal (investigational) product, whether or not related to the medicinal (investigational) product.

AEs also include: any worsening compared to baseline (i.e., any clinically significant change in frequency and/or intensity) of a pre-existing condition that is temporally associated with the use of the study drug; abnormal laboratory findings considered by the reporting investigator to be clinically significant.

A treatment-emergent AE (TEAE) is defined as any event not present before exposure to study drug or any event already present that worsens in either intensity or frequency after exposure to study drug.

The condition of subjects will be monitored from time of signing the ICF through the EOS Visit. In addition, subjects will be observed for any signs or symptoms and asked about their condition by open questioning, such as "How have you been feeling since you were last asked?", at every study visit from the Screening Visit through the EOS Visit.

All non-serious AEs, whether volunteered, elicited, or noted on the physical examination, and SAEs will be recorded from the Screening Visit (signing the ICF) through the EOS Visit. The AE information collected during the period from the Screening Visit until study drug administration on Day 1 is intended only for establishing a baseline status for subjects and for recording any screening procedure-related AEs. The nature, time of onset, duration, and severity of all AEs, both serious and non-serious, will be documented, together with an Investigator's opinion of the relationship to study drug administration.

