#### **8.7.1 Adverse Events**

Adverse events will be mapped to preferred term (PT) and system organ class (SOC) using the most up to date Medical Dictionary for Regulatory Activities (MedDRA). AEs that begin after the first administration of study drug or existing AEs that worsen after the first dose of study medication are considered TEAEs. The number and percentage of subjects reporting TEAEs will be summarized for each treatment group by MedDRA SOC and PT, by severity, and by relationship to study treatment. The number and percentage of subjects with serious AEs, and the number and percentage of subjects with AEs leading to treatment

discontinuation will also be summarized for each treatment group by MedDRA system organ class and preferred term.

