1.2. Study Design

This is a randomized, double-blind, placebo-controlled study to investigate the efficacy, safety, tolerability, PK, and immunogenicity of KPL-716 administered SC in subjects with moderate to severe PN experiencing severe pruritus.

[figure not shown]
The Phase 2b study ([Figure 1](#)) consists of a 4-week screening period and a 16-week double-blind (DB) period, followed by a 36-week open-label-extension (OLE) period. Approximately 180

subjects with moderate to severe PN experiencing severe pruritus will be randomized (at 1:1:1:1 ratio) into one of the following 4 arms:

- Arm A: KPL-716, 540 mg, SC, every 4 weeks (Q4W)
- Arm B: KPL-716, 360 mg, SC, Q4W
- Arm C: KPL-716, 120 mg, SC, Q4W
- Arm D: Placebo, SC, Q4W

A total of 4 doses of study drug will be administered during the DB Period to measure the efficacy, safety, and PK of KPL-716.

Figure 1 Phase 2b Study Design Diagram

After the DB period, all subjects will have the option to receive KPL-716 360 mg SC, Q2W during the OLE period to evaluate the long-term safety and PK of KPL-716. For subjects who complete the DB period but choose not to participate in OLE, or who terminate earlier, an End of Study (EOS) visit will be required 4 weeks following the date of last study drug dose.

Subjects will follow the schedule below:

- Screening period (minimum 7 days and maximum 28 days)
- DB period (Day 1 [Baseline] to Week 16)
- OLE period (End of Week 16 to Week 52)

The allowable visit window from Week 2 to Week 16 is \pm 2 days and thereafter to Week 52 is \pm 3 days.

Randomization and Dosing:

Subjects will be randomized 1:1:1:1 into one of the following 4 arms: KPL-716 540 mg SC, Q4W; KPL-716 360 mg SC, Q4W; KPL-716 120 mg SC, Q4W; or placebo SC, Q4W. At the end of DB period, all subjects will have the option to enter the OLE period to receive KPL-716

360 mg SC Q2W. Stratification will be performed based on sex and years since first nodule observed (i.e., ≥ 10 years vs. < 10 years).

Efficacy Assessments:

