1.3.2. Safety Endpoints

- Incidence rate and severity of treatment-emergent adverse events (TEAEs)
- Incidence rate and severity of study drug-related TEAEs
- Vital signs, electrocardiogram (ECG), and clinical laboratory test results

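### TEAE percentages for the 16-week double-blind period and the 36-week open-label extension are not comparable, and no exposure-adjusted measure is planned

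*SAP*

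**What the plan says.** The safety endpoint in SAP 1.3.2 (and Protocol 3.4) is "Incidence rate and severity of treatment-emergent adverse events (TEAEs". Neither document defines incidence rate.

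SAP 4.7.1 splits events at the first open-label dose: "TEAEs which occur (based on AE start dates) before OLE first dose date will be summarized into DB period, otherwise into OLE period". It then lists the overview categories: any, drug-related, serious, leading to discontinuation, of special interest, and so on. It names no measure for them. The measure comes from two other places. Protocol 8.7.1 says: "The number and percentage of subjects reporting TEAEs will be summarized for each treatment group by MedDRA SOC and PT". SAP section 3 prescribes counts and percentages for all categorical variables.

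Protocol 4.2 gives the period lengths: "16 weeks for the Double-Blind Period, and 36 weeks for the OLE Period". SAP 1.2 and 4.5 give four double-blind doses and up to 17 open-label doses. SAP 1.2 says that the extension is there to evaluate long-term safety and PK.

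SAP 4.5 derives weeks of treatment for each period, and SAP 4.1 derives the length of each period. Neither is linked to adverse events. SAP 4.7 bases safety summaries on the safety analysis set. SAP 2.5 defines an OLE analysis set, but no section assigns it to the open-label TEAE tables.

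**The concern.** A percentage of subjects with an event grows with the time over which they are watched. The plan puts one such percentage over 16 weeks and another over 36 weeks into the same safety report, and says neither how to relate them nor which denominator the second one uses.

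The comparison is one that the documents invite. Protocol 4.5 describes the open-label regimen as giving higher drug concentrations than the blinded regimens, assumes it to be at least as safe as the Phase 2a exposures, and treats the extension as part of the search for an effective and safe dose. Someone reading the tables with that in mind will set the open-label column beside the double-blind columns. A higher percentage could then be taken as toxicity of the open-label regimen when it reflects only longer observation. A similar percentage could hide a real difference if many subjects left the extension early or never entered it.

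Ascertainment may differ too. At each visit subjects are "asked about their condition by open questioning", and there are 5 post-dose visits in the double-blind period against 17 in the extension.

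**Working it through.** **Reproducing the plan's durations.** Protocol 4.2 states: "The planned study duration per subject for Phase 2b will be approximately 56 weeks". The parts add up: 4 + 16 + 36 = 56. The visit days in Protocol Appendix 1 agree: (113 − 1)/7 = 16.0 weeks and (365 − 113)/7 = 36.0 weeks. Open-label doses run from Week 16 to Week 48 every 2 weeks, so (48 − 16)/2 + 1 = 17, as in SAP 4.5. Post-dose visits are Weeks 2, 4, 8, 12 and 16 (5), against Weeks 18 to 48 every 2 weeks plus Week 52 (16 + 1 = 17). The ratio of planned lengths is 36/16 = 2.25.

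**Percentages at an unchanged rate.** The documents give no TEAE rate for this trial, so a range is assumed. Take a constant rate λ per subject-year that is the same in both periods, complete follow-up, and the subjects entering each period as its denominator. The expected percentage with at least one event is 1 − exp(−λ × weeks/52).

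| Assumed rate per 100 subject-years | DB, 16 weeks | OLE, 36 weeks | Ratio |
|---|---|---|---|
| 50 | 1 − exp(−0.154) = 14.3% | 1 − exp(−0.346) = 29.3% | 2.05 |
| 100 | 1 − exp(−0.308) = 26.5% | 1 − exp(−0.692) = 50.0% | 1.89 |
| 200 | 1 − exp(−0.615) = 46.0% | 1 − exp(−1.385) = 75.0% | 1.63 |

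As λ tends to 0 the ratio tends to 2.25. Relative distortion is therefore greatest for rare events, the group in which serious and special-interest events would usually fall.

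**What would remove or reverse the excess.**

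- *A lower open-label rate.* The percentages are equal when the OLE rate is 16/36 = 0.44 of the DB rate, and below that the order reverses. At a DB rate of 100 and an OLE rate of 30, the figures are 26.5% against 1 − exp(−0.3 × 36/52) = 18.8%.
- *Dropout.* At equal rates, if follow-up in the extension averaged about 16 weeks, the excess would be roughly gone.
- *The safety set as open-label denominator.* Non-entrants then count as subjects without an event. The percentages are equal when the fraction entering the extension is the inverse of the ratio above: 14.3/29.3 = 49%, 26.5/50.0 = 53% and 46.0/75.0 = 61%. With higher entry the OLE figure still exceeds the DB figure, and with lower entry it falls below.

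**What an exposure-adjusted rate does under the same assumptions.** Expected first events per subject are 1 − exp(−λT). Expected time at risk to first event or period end is (1 − exp(−λT))/λ. Their quotient is λ for any T. At a rate of 100, DB gives 0.265 events over 0.265 years and OLE gives 0.500 over 0.500, which is 100 per 100 subject-years in both.

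**The case against.** The strongest reply is that no document plans a DB-versus-OLE safety contrast. SAP section 3 confines inference to each dose against placebo, and the extension is descriptive. Percentages of subjects are standard. The report will also carry treatment duration and number of doses by period (SAP 4.5), period duration and reasons for discontinuation (SAP 4.1), and subject listings, so an attentive reader would see that follow-up differs. This stands as a reason not to rate the point higher. It does not supply the missing measure, because summary durations do not give time at risk to first event for each event category.

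Three stronger readings are tempting, and the documents do not support them.

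- A reader might infer that open-label percentages must be higher. That needs an equal rate, similar retention and an entrant denominator, and none of these is given. Entry is optional, and SAP 4.7 names the safety set, which would dilute the open-label figures.
- A reader might infer that the incidence-rate endpoint is not delivered. The term is undefined, and this SAP uses incidence for subjects counted once (4.2.3, 4.3.2) and for subject-level laboratory and QTcF findings (4.7.2, 4.7.4). On that usage a percentage delivers it. Only a person-time rate is missing.
- A reader might infer that the randomized safety comparison is biased. All four arms have the same planned 16 weeks, so it is largely unaffected. Unequal dropout between arms could still make follow-up differ. So could subjects not enrolled in the extension, whose DB safety period runs to end of study under SAP 3.3.

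The visit-frequency point cannot be sized. Adverse-event monitoring is continuous from screening to end of study, and Protocol Appendix 1 allows remote collection at most open-label visits for subjects who self-administer.

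**Conclusion.** The point holds as one of comparability and specification. TEAEs are divided between periods planned at 16 and 36 weeks, only counts and percentages of subjects are stated, the open-label denominator is not settled, and exposure is derived but not used for adverse events. The excess of 1.63 to 2.05, with its limit of 2.25, rests on assumed rates of 200 to 50 per 100 subject-years, a constant and equal hazard, full follow-up and entrants as denominator. It shows how far apart two percentages can be with no change in risk. It does not predict this trial's result, and the direction can reverse. This is a worthwhile, inexpensive improvement to the safety reporting and does not threaten the main comparison.

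**What to change.** In SAP 4.7.1:

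- Keep the planned percentages, and name the OLE analysis set (SAP 2.5) as the denominator for open-label TEAE tables.
- Add, by period, subjects with a first event in that period per 100 subject-years at risk, with 95% CI. Do this for any TEAE, drug-related TEAEs, serious TEAEs, events of special interest, and TEAEs leading to discontinuation.
- Define time at risk as running from the first dose of the period to the first event, or to the end of the period under the safety definitions in SAP 3.3. The treatment durations in SAP 4.5 are not suitable, because they are capped at 27 or 13 days after the last dose, while events are counted to the end of the period.
- For any statement that compares the two periods, also show events in the first 16 open-label weeks, which matches the planned double-blind length.
- State whether incidence rate in the endpoint means a proportion of subjects or a person-time rate.

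The cost is one more derivation and a few table columns. It uses event start dates, dose dates and period end dates that the SAP already relies on, so no new data are needed. The limitation is that a first-event rate summarizes well only when the hazard is roughly constant, which the 16-week window helps to check. Neither measure makes the two periods a randomized comparison: entrants are self-selected and the regimen changes.
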